6.2 Schedule of Assessments: SL-172154 + MIRV Cohorts (Dose Escalation and Dose Expansion)

Cycle Length = 21 days	PreScrn	Scrn ^a	CYCLE 1 (C1)				CYCLE 2 (C2)			CYCLE 3 (C3) and Subsequent Cycles			PTV ^u	SFU ^v
			D1	D8	D9	D15	D16-22	D1	D8	D15	D1	D8	D15	
Assessment ^b														
Informed consent	X	X												
Eligibility criteria		X ^c	X											
Demographics		X												
FFPE archival tumor tissue and/or new biopsy for FR ^d	X													
Medical and disease history		X												
Cancer treatment history		X												
Type and screen (ABO/Rh), Blood phenotyping, DAT ^d		X												
TSH, free T4 ^e		X												
Antiviral testing ^f (HBV/HCV)		X												
Record historical BRCA, HRD status (if known)		X												
12-lead ECG ^g		X												
ECHO/MUGA ^h		X												
Ophthalmic exam ⁱ		X									← prior to C3, C5, C7 →		X	
Physical examination ^j	X	X	X			X		X		X				X
Vital signs ^k	X	X	X			X		X	X	X	X	X		
Pulse oximetry ⁱ	X	X	X			X		X	X	X	X	X		
Height (screening only) / weight	X	X						X		X				
ECOG performance status		X	X	X		X		X		X				X
Ocular symptom assessment ^j		X	X					X		X				X
Pregnancy test ^k (serum or urine, FCBP only)		X									X ^k			X
Clinical chemistry ^l		X	X	X	X	X		X	X	X	X			X
Hematology ^l		X	X	X	X	X		X	X	X	X			X
Coagulation ^l (PT, aPTT, INR, d-dimer, fibrinogen)		X				X								

Cycle Length = 21 days	PreScrn	Scrn ^a	CYCLE 1 (C1)				CYCLE 2 (C2)			CYCLE 3 (C3) and Subsequent Cycles			PTV ^u	SFU ^v
			D1	D8	D9	D15	D16-22	D1	D8	D15	D1	D8	D15	
Assessment ^b														
Ferritin		X			X									
C-reactive protein		X												
Haptoglobin		X			X									
Blood sample for SL-172154 PK ^m				X	X	X			X					
Blood sample for SL-172154 ADA ^m				X		X			X			X ^{m1}		X ^{m2}
Blood sample for cytokines ⁿ				X	X	X								
Blood sample for receptor occupancy ⁿ				X	X	X								
Blood sample for MIRV PK ^m			X						X			X		X
Blood sample for MIRV ADA ^m			X						X			X		X
Scans for disease assessment ^o	X										X ^o		X ^o	
CA-125 ^o		X									X ^o		X ^o	
Tumor biopsy ^q		X					X ^q							
SL-172154 administration ^r			X		X				X	X	X	X	X	
MIRV administration ^s			X					X			X			
Concomitant medications		X	Continuous Monitoring During Treatment Phase of the Study										X	
Adverse events ^t	X	X	Continuous Monitoring During Treatment Phase of the Study										X	
Survival contact ^v (q3 months ± 14d)														X

Abbreviations: ADA = anti-drug antibodies; AE = adverse event; aPTT = activated partial thromboplastin time; BCVA = best corrected visual acuity; C = cycle; CT = computed tomography; CTCAE = Common terminology criteria for adverse event; D=day; DAT = direct antiglobulin test; DLT = dose limiting toxicity; ECG = electrocardiogram; ECHO = echocardiogram; ECOG = Eastern Cooperative Oncology Group; eCRF = electronic case report form; FCBP = female of childbearing potential; FFPE = formalin fixed paraffin embedded; FR α = folate receptor alpha; HBV = hepatitis B virus; HCV = hepatitis C virus; HRD = homologous recombination deficiency; INR = international normalized ratio; IOP = intra-ocular pressure; IRR = infusion-related reaction; MIRV = mirvetuximab soravtansine; MUGA = multigated acquisition scan; NCI = National Cancer Institute; PD = pharmacodynamics; PK = pharmacokinetics; PreScrn = prescreening; PT = prothrombin time; PTV = post-treatment visit; q = every; SAE = serious adverse event; Scrn = screening; SFU = survival follow-up; TSH = thyroid stimulating hormone

a. **Screening:** Screening Period extends from Day -21 to Day -1 for routine clinical assessments unless otherwise specified; subjects may complete Screening and initiate dosing on the same day provided all Screening assessments are completed and confirmed to meet eligibility requirements prior to receipt of MIRV or SL-172154. The following screening assessments do not need to be repeated pm Cycle 1 Day 1 if performed within 72 hours of the first dose of study treatment: hematology, clinical chemistry, coagulation panel, ECOG status, and physical exam.

	
Baseline CT or positron emission tomography (PET)/CT or Magnetic resonance imaging (MRI) tumor assessments are required for all subjects within 28 days prior to the first dose of study treatment.

b.	
Assessment Window: With the exception of Screening assessments and unless otherwise specified, assessments performed at \leq 4-week intervals will have a \pm3-day window and assessments performed at $>$ 4-week intervals will have a \pm1-week window. No assessment window is permitted during the DLT-evaluable period in the dose escalation cohorts.

c.	
Eligibility Evaluation: Subjects must meet eligibility criteria prior to first dose of study treatment.

d.	
Blood Phenotyping (ABO/Rh) and DAT: will be performed at local laboratories according to the laboratory's normal procedures. At screening the following tests will be performed: a) ABO and D group (ABO/Rh) type and antibody screen and antibody identification if required, b) DAT, and c) phenotype/genotype for, at a minimum, the minor antigens Rh C/c, E/e, K, Jk, Fy, and MNS. If assessment was performed within 21 days of the first dose of study treatment and all requested information is available, this can be used for baseline assessment

e.	
ECG: 12-lead electrocardiogram (ECG) must be performed at screening to serve as a baseline for comparison in the event of a cardiac AE/SAE during the study. ECG is to be performed within 30 days of the first dose of study treatment.

f.	
ECHO/MUGA: ECHO or MUGA is to be performed at screening to serve as a baseline for comparison in the event of a cardiac AE/SAE during the study. ECHO/MUGA is to be performed within 30 days of the first dose of study treatment. The same methodology should be used at each assessment.

g.	
Ophthalmic Exam: Ophthalmic examinations will be performed in all subjects by an ophthalmologist, optometrist, or other qualified health care provider ("eye care professional") within 21 days before C1D1 (baseline) and at PTV (+/- 14 days) and will include the following: manifest refraction, BCVA, IOP assessment, fundoscopy baseline and PTV only), and slit lamp examination. If a subject receiving MIRV develops new ocular symptoms of CTCAE $>$ Grade 1, that subject is required to have a complete examination conducted by an eye care professional prior to next MIRV administration. All subjects receiving MIRV, regardless of reporting symptoms, are required to have ophthalmological exams including BCVA, IOP, and slit lamp exam prior to Day 1 dosing in Cycle 3, 5, and 7. For subjects with ongoing keratitis/keratopathy, a cornea epithelial defect, or \geq 3-line loss in BCVA after end of treatment with MIRV, an ophthalmic examination should be done every 30 days until resolution, stabilization, or return to baseline. Ocular symptoms (blurred vision, etc.) should also be assessed at this time. Subjects requiring an ophthalmological examination due to symptoms prior to Cycle 2 or 4 will then proceed to every other cycle (approximately 6 weeks) exams as indicated by findings and do not require the routine, asymptomatic exams at Cycle 3, 5, and 7.

h.	
Physical Examination: A full physical exam is required only at screening and PTV. Physical exams should be performed per standard of care during the on-treatment period.

i.	
Vital Signs and Pulse Oximetry: Blood pressure (BP), heart rate (HR), temperature (T) and respiratory rate (RR) must be measured after the subject has been sitting for at least five minutes (min). Pulse oximetry will be collected to coincide with vital sign time points noted below.
 
1. Collect vital signs/pulse oximetry on Day 1 of every Cycle at Predose (within 60 min of starting the MIRV infusion); postinfusion vital signs should be collected as clinically indicated for potential infusion-related reaction.2. Collect vital signs/pulse oximetry during Cycle 1 on Day 8 and Day 15: Predose (within 60 min of starting the SL-172154 infusion), at the end of infusion (EOI; \pm 5 min) and then 0.5 hour [hr] (\pm 5 min), 2 hr (\pm 10 min), and 4 hr (\pm 10 min) after end of infusion (EOI) of SL-172154.3. Collect vital signs/pulse oximetry on Day 8 and Day 15 of Cycle 2 and in each subsequent cycle: Predose (within 60 min of starting the infusion) and at the end of infusion [EOI] (\pm 5 min) of SL-172154.4. For subjects experiencing any grade IRR, refer to Section 3.7.1.1 for schedule of vital signs that should be measured at time of the IRR event.
j.	
Ocular Symptom Assessment: will be performed by the treating physician or other qualified individual before the start of each cycle for all subjects. For subjects receiving MIRV reporting new CTCAE $>$ Grade 1 ocular symptoms, treatment will be held until the subject is evaluated by an eye care professional for a complete examination. Refer to Table 8 and Table 9 for additional details on management of ocular findings on study.

k.	
Pregnancy Test: A serum pregnancy test (beta-human chorionic gonadotropin [β-hCG]) or urine pregnancy test must be performed at screening for all FCBP within 4 days of the first dose of MIRV on Cycle 1 Day 1. Repeat this test every 6 weeks during study treatment (i.e., C3D1, C5D1, C7D1, etc.) and at PTV. Contraception should be continued for at least 3 months after the last dose of either SL-172154 or MIRV.

l.	
Hematology/ Clinical Chemistry/ Coagulation/ TSH/ Free T4/ Antiviral Testing: will be performed at local laboratories according to the laboratory's normal procedures. Required laboratory tests are provided in Section 6.5.9.

m. **Pharmacokinetic (PK) / Anti-Drug Antibody (ADA):** Blood sample collection timings for SL-172154 PK/ADA and MIRV PK/ADA measurement are outlined in Section 6.2.1. Blood volumes required will be provided in the Study Lab Manual (SLM). PK/ADA samples should not be collected from infusion port for drug delivery i.e., recommend having a separate line in the opposite arm for sample collection.

1. If a subject discontinues SL-172154 due to IRR and continues on MIRV monotherapy, to the extent feasible, an additional ad-hoc ADA sample should be collected at a subsequently scheduled visit.
2. All subjects should have just one additional blood sample collected for SL-172154 ADA assessment within 45-90 days of last dose of SL-172154 study treatment.

n. **Cytokines and receptor occupancy:** Blood sample collection timing for cytokine and receptor occupancy assessments are outlined in Section 6.2.1. Blood volumes required will be provided in the SLM. Cytokine samples should not be collected from infusion port for drug delivery, i.e., recommend having a separate line in the opposite arm for sample collection.

o. **Scans for Disease Assessment and CA-125:** Baseline tumor assessments are required for all subjects within 28 days prior to the first dose of study treatment. CA-125 should also be obtained at screening within 28 days of first dose of SL-172154. Baseline and on-treatment tumor assessments for all tumor types by RECIST v1.1 should include CT with contrast of chest, abdomen, and pelvis and other known sites of disease at each time point. Bone scan, positron emission tomography (PET)/CT, and/or MRI should be performed only if clinically indicated. Tumor assessments must be performed at screening and at the following intervals until radiologic disease progression: during the last week of every even cycle (Days 16 to Day 22) every 2 cycles/ 6 weeks \pm 1 week through Cycle 18, every 3 cycles/ 9 weeks \pm 1 week up to Cycle 27, and then every 4 cycles/ 12 weeks \pm 1 week up to conclusion of the study. Subjects who discontinue study treatment for reasons other than disease progression (e.g., AE or withdrawal of consent) will be monitored for radiologic response until start of another anti-cancer therapy, disease progression, withdrawal of consent, or death. CA-125 should be measured to coincide with each scheduled radiographic tumor assessment as outlined above with the last required assessment of CA-125 performed at the PTV which occurs 30 days (\pm 7 days) after the last dose of study treatment. If there is more than one week delay in any cycle, please perform all the subsequent disease assessments per schedule in weeks.

p. **FR_a Expression Screening on Archival Tumor Tissue or Fresh:** Archival tissue will be collected from all subjects after signing the prescreening consent (if separate from the main study consent). The prescreening period is not time limited. Central testing for positive FR_a expression is required for all subjects to determine eligibility. All subjects must submit archival tumor tissue block or fresh cut slides from available block (FFPE slides). Those who do not have archival tumor tissue to submit will be required to undergo procedure to obtain a new biopsy using low-risk, medically routine procedure during the Prescreening period to confirm eligibility. If the archival tumor tissue does not meet FR_a criteria, a new biopsy tumor sample may be submitted and used to confirm this criterion.

q. **Tumor Biopsy:** Paired biopsies for exploratory PD analysis are required (pre- and on-treatment) to be obtained in subjects enrolled in the dose expansion cohort who have tumor accessible to core-needle biopsy and for whom there is an acceptable level of risk as per investigator assessment. Biopsies will be obtained at Screening (to evaluate the immune status of the tumor before SL-172154 treatment) and on or between Day 16 through Predose on Day 1 of Cycle 2.

r. **SL-172154 Administration:** Subjects will be monitored prior to and during each SL-172154 infusion. SL-172154 should be administered according to the prescribed dosing schedule in Cycle 1 to align with the safety DLT assessment and sample (PK, ADA, etc.) collection schedules. Beginning on Cycle 2 Day 8, a window of \pm 2 days is allowed for scheduled dosing days for drug administration (NOTE: each dose must be administered at least 5 days apart from the previous dose). If the start of a subsequent cycle (e.g., Day 1) is delayed, the current cycle length is extended (e.g., the cycle lasts longer than 21 days). The doses of SL-172154 in that cycle are not delayed (e.g., administered on Day 8, 15).

s. **MIRV Administration:** MIRV will be administered according to the dosing schedule provided. If the start of a subsequent cycle (e.g., Day 1) is delayed, the current cycle length is extended (e.g., the cycle lasts longer than 21 days). The length of subsequent cycles will remain unchanged (i.e., 21 days for MIRV Cohort).

t. **AE Monitoring:** Subjects will be followed continuously for AEs during the study and for 30 days after the last dose of study treatment. After a subject is discontinued from study treatment due to progressive disease or for other reasons, any ongoing AE should be followed until resolution (or return to baseline) and documented in the eCRF. If another anti-cancer agent is started within 30 days after the last dose of study treatment, only SAEs and AEs that occur prior to the start of the new anticancer therapy should be recorded. In the event of a continuing SAE, the subject should be asked to return for follow-up until the SAE has resolved or is deemed to be continuing indefinitely. AEs will be characterized per NCI-CTCAE criteria v5.0 and events recorded in the eCRF.

u. **Post-Treatment Visit (PTV):** visit should occur 30 days (\pm 7 days) after the last dose of study treatment. If the subject is going to start a new anticancer therapy before the PTV due date, PTV should be conducted prior to starting the new therapy.

v. **Survival Follow-Up (SFU):** All subjects will be contacted after discontinuing study treatment to collect survival status. Subjects should be contacted every 3 months (± 14 days) from the PTV until death, withdrawal of consent, lost to follow-up or end of study. Contact may include clinic visit, telephone contact, email or mail, chart review, or obituary notice to document survival status. Initiation of any subsequent anti-cancer therapy should also be reported.

6.2.1 PK, ADA, Cytokines and Receptor Occupancy (SL-172154 + MIRV Dose Escalation and Dose Expansion Cohorts)

CYCLE 1	C1D1			C1D8								C1D9	C1D15						
	Predose ¹	EOI ²	2h post EOI	Pre-dose ¹	EOI ²	0.5h post EOI	1h post EOI	1.5h post EOI	2h post EOI	4h post EOI	6h post EOI		Pre-dose ¹	EOI ²	0.5h post EOI	1h post EOI	1.5h post EOI	2h post EOI	4h post EOI
Blood sample for SL-172154 PK ^{3,4,5,6}				X	X	X	X	X	X	X	X	X	X	X	X	X	X	X	X
Blood sample for SL-172154 ADA ⁶				X									X						
Blood sample for MIRV PK [D1 of each cycle] ⁶	X	X																	
Blood sample for MIRV ADA, neutralizing antibodies [D1 of each cycle] ⁶	X																		
Blood sample for cytokines ^{3,5} (during dose escalation and for approximately 25 subjects in dose expansion)				X					X			X	X					X	
Blood sample for Receptor Occupancy ^{3,5} (during dose escalation and for approximately 25 subjects in dose expansion)				X			X					X	X		X				

CYCLE 2	C2D8								C3D8 and onwards in every cycle ⁷
	Predose ¹	EOI ²	0.5h post EOI	1h post EOI	1.5h post EOI	2h post EOI	4h post EOI	6h post EOI	
Blood sample for SL-172154 PK ^{3,4,6}	X	X	X	X	X	X	X	X	
Blood sample for SL-172154 ADA ⁶	X								X

Abbreviations: ADA = anti-drug antibodies; C = cycle; D = day; EOI = end of SL-172154 infusion; IRR = infusion-related reaction; MIRV= mirvetuximab soravtansine; PK = pharmacokinetics

Note: Please refer to [Table 2](#) for infusion duration for the assigned SL-172154 dose

1. Predose samples should be collected within 60 minutes prior to the start of the MIRV infusion or the SL-172154 infusion.
2. EOI samples should be collected ± 5 min from the end of the MIRV infusion or the SL-172154 infusion.
3. Any sample collected 1h to less than 4h post-EOI of SL-172154 will have ± 10 min window.
4. Any sample collected 4h to 6h post-EOI of SL-172154 will have ± 30 min window.
5. 24h post-EOI sample will have ± 2 h window.
6. Samples for MIRV PK, MIRV ADA, and SL-172154 ADA will also be collected at the PTV. All subjects should have just one additional blood sample collected for SL-172154 ADA assessment within 45-90 days of the last dose of SL-172154 study treatment.
7. If a subject discontinues SL-172154 due to IRR and continues on MIRV monotherapy, to the extent feasible, an additional ad-hoc ADA sample should be collected at a subsequently scheduled visit.

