6.11 Assessment of Anti-Tumor Activity

The primary analysis of anti-tumor activity will be assessed according to RECIST v1.1 for solid tumors using CT with contrast of chest, abdomen, and pelvis and other known sites of disease. Bone scan, positron emission tomography (PET)/CT, and/or MRI should be performed only if clinically indicated. Tumor assessments must be performed at screening and at the following intervals until radiologic disease progression:

- SL-172154 + PLD: during the last week (Day 22 to predose on Day 29) of every 2 cycles/ 8 weeks±1 week through Cycle 6, and every 3 cycles/ 12 weeks ±1 week thereafter up to year 2 and then every 6 cycles/ 24 weeks ±1 week up to study conclusion. If there is more than one week delay in any cycle, please perform all the subsequent disease assessments per schedule in weeks.
- SL-172154 + MIRV: during the last week (Day 16 to predose on Day 22) of every 2 cycles / 6 weeks±1 week through Cycle 18, and every 3 cycles/ 9 weeks±1 week thereafter through Cycle 27, and every 4 cycles/ 12 weeks±1 week until study conclusion. If there is more than one week delay in any cycle, please perform all the subsequent disease assessments per schedule in weeks.

Refer to Section 8 for additional details.

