
Section 6.1; 6.2 Schedules of assessments; Section 6.11 Assessment of Anti-Tumor Activity (changes applicable from version 2.0 and 2.1 to version 3.0)
	
Description of Change: Text was revised to allow disease assessments to be performed per schedule in Weeks instead of treatment Cycles
 
Rationale/Justification: Per the protocol, disease assessment scans should be performed at screening and during the last week of scheduled Cycle (Cycle 2, 4 etc.) until radiologic disease progression. However, delays in treatment Cycles due to adverse events have resulted in scan delays for several subjects. To avoid this issue, if there is more than one week delay in any Cycle, all the subsequent disease assessments can be performed per schedule in Weeks. This information was also communicated to the Investigators in a clarification memo dated 18-Apr-2024.

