7.2 Clinical Benefit Rate

For SL-172154 + PLD regimen, the CBR based on RECIST 1.1 is defined as the proportion of subjects whose best overall response is a confirmed CR, confirmed PR or SD \geq 16 weeks, where SD \geq 16 weeks is defined as at least one SD or better for \geq 15 weeks (16 weeks with 1 week visit window) and not qualifying for a confirmed CR or PR as in Table 6.

Table 6 Best overall response of SD \geq 16 weeks in SL-172154 + PLD regimen

Response at Week 8 assessment	Response at Week 16 assessment	Response at Week 24 assessment	SD \geq 16 weeks
----------------------------------	-----------------------------------	-----------------------------------	--------------------

SD	SD/PR/CR	Any	Yes
SD	PD	Any	No
SD	NE/missing	SD/PR/CR	Yes
SD	NE/missing	PD/NE/missing	No
CR/PR	PD	Any	No
PR	SD	Any	Yes
NE	SD	Any	Yes

For SL-172154+MIRV regimen, the CBR based on RECIST 1.1 is defined as the proportion of subjects whose best overall response is a confirmed CR, confirmed PR or SD \geq 12 weeks, where SD \geq 12 weeks is defined as at least one SD or better for \geq 11 weeks (12 weeks with 1 week visit window) and not qualifying for a confirmed CR or PR as in Table 7.

Table 7 Best overall response of SD \geq 12 weeks in SL-172154 + PLD regimen

Response at Week 6 assessment	Response at Week 12 assessment	Response at Week 18 assessment	SD \geq 12 weeks
SD	SD/PR/CR	Any	Yes
SD	PD	Any	No
SD	NE/missing	SD/PR/CR	Yes
SD	NE/missing	PD/NE/missing	No
CR/PR	PD	Any	No
PR	SD	Any	Yes
NE	SD	Any	Yes

The CBR will be estimated with a 95% CI using the exact probability method. Summary of CBR will be provided for the All Treated population and Response Evaluable population.

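### Tumour scans have both a cycle anchor and a week anchor, and the rule that chooses between them is silent on short cycle delays that add up

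*Protocol*

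**What the plan says.** Protocol 6.2 footnote o puts MIRV scans "during the last week of every even cycle (Days 16 to Day 22) every 2 cycles/ 6 weeks", with a one-week window. Section 6.11 puts PLD scans "during the last week (Day 22 to predose on Day 29) of every 2 cycles/ 8 weeks±1 week through Cycle 6", and 6.1 footnote m agrees. Each sentence therefore carries a cycle-day anchor and a week anchor.

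On late cycles, 6.2 footnote r says: "If the start of a subsequent cycle (e.g., Day 1) is delayed, the current cycle length is extended". Protocol 6 (opening bullets), 6.1 footnote o and 6.2 footnote s add that later cycles keep their normal length, so lost days are not recovered. The switch to weeks is the same sentence in 6.1 footnote m, 6.2 footnote o and 6.11: "If there is more than one week delay in any cycle, please perform all the subsequent disease assessments per schedule in weeks". Section 16.10 gives the reason for it: "delays in treatment Cycles due to adverse events have resulted in scan delays for several subjects".

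On the analysis side:
- SAP 7.2 scores CBR from assessments labelled Week 8/16/24 (PLD) and Week 6/12/18 (MIRV).
- SAP 5.2 reports data by nominal visit without windowing.
- SAP 7.5 dates PFS by the actual date of progression or death, but takes its rule on two or more consecutive missed scans from the protocol's Section 6 schedule with a one-week window.

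**The concern.** The Version 3.0 repair covers a cycle that slips by more than a week. It does not mention several shorter slips. On the literal wording these leave the subject on the cycle calendar while the scans move away from the weeks that the SAP uses.

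Three things are at stake. Scan timing becomes linked to toxicity, since holds of PLD or MIRV are what delay a cycle. A subject who is stable at Week 12 or 16 but progresses before a drifted scan is first seen as PD at that scan, and can lose the SD that CBR requires. And a programmer applying the missed-scan rule has to choose an anchor, because Section 6 supplies two.

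These endpoints are secondary, but Protocol 3.4 uses preliminary efficacy to judge whether a regimen goes to Phase 2. There is no control arm, and the FRα subgroups have about 20 subjects each.

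**Working it through.** **Plan's own figures.** SAP 7.1 sets the minimum SD interval at the first nominal scan minus 7 days: 6 × 7 − 7 = 35 days (MIRV) and 8 × 7 − 7 = 49 days (PLD). Both reproduce, and both rest on the week calendar.

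**Inputs.** Cycle length L = 21 (MIRV) or 28 (PLD) days. Scan week = Days 16–22 (MIRV) or Days 22–29 (PLD) of even cycles. Nominal scan at the end of cycle c = c × L, ±7 days. The delay per cycle start, d, is an assumption, because the documents give none. The first delayed start is C3D1 if Section 6 (beginning with Cycle 2) is read strictly, or C2D1 on the footnotes' wording.

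**Drift.** Drift at cycle c = (number of delayed starts up to c) × d. For Cycle 4 that is 2 or 3 starts; for Cycle 6 it is 4 or 5. Day 1 of cycle c = 1 + (c − 1) × L + drift.

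Example, MIRV Cycle 4 with two 7-day slips: C4D1 = 1 + 63 + 14 = 78, so Days 16–22 are study days 93–99. With three slips, C4D1 = 85 and the scan week is days 100–106.

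| Scan | Nominal day (window) | Scan week, d = 7 | Drift, d = 7 | Drift, d = 3 |
|---|---|---|---|---|
| MIRV Cycle 4 (Week 12) | 84 (77–91) | 93–99 or 100–106 | 14–21 days | 6–9 days |
| MIRV Cycle 6 (Week 18) | 126 (119–133) | 149–155 or 156–162 | 28–35 days | 12–15 days |
| PLD Cycle 4 (Week 16) | 112 (105–119) | 120–127 or 127–134 | 14–21 days | 6–9 days |
| PLD Cycle 6 (Week 24) | 168 (161–175) | 190–197 or 197–204 | 28–35 days | 12–15 days |

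At d = 2 the drift is 4–6 days (second scan) and 8–10 days (third). The first scan moves by at most one slip, 7 days, and stays in window.

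**Missed-scan rule.** A MIRV scan on days 93–106 lies in neither the Week 12 window (77–91) nor the Week 18 window (119–133). On the cycle anchor it is the scheduled scan; on the week anchor Week 12 was missed.

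**Illustration of direction.** Assume exponential progression times with median 3.7 months (the upper end of the 2.1 to 3.7 months that the protocol quotes for single-agent PLD), progression seen only at scans, and every start from C2D1 7 days late. Then S(t) = 2^(−t/112.6), with 3.7 × 30.4375 = 112.6 days.
- Without PD at the scan that decides CBR: MIRV S(84) = 0.60 becomes S(105) = 0.52; PLD S(112) = 0.50 becomes S(133) = 0.44.
- 4-month PFS rate (day 121.75), set by the last scan before it: MIRV 0.60 becomes 0.52; PLD S(112) = 0.50 becomes S(63) = 0.68, because the second scan moves past the landmark.
- Observed median PFS: MIRV 4.14 becomes 5.29 months; PLD 5.52 becomes 4.37 months.

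The signs differ because drift can also bring a scan closer to an event. MIRV progression on day 90 is first seen on day 126 on schedule, but on day 105 with drift.

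**The case against.** The strongest reply is that the same sentences state 6 or 8 weeks ±1 week, and the assessment-window footnote (b) repeats a one-week window for assessments more than 4 weeks apart. Two 7-day slips between scans make the interval 42 + 14 = 56 days (MIRV) or 56 + 14 = 70 days (PLD), outside that limit. The text therefore conflicts with itself; it does not plainly permit the drift. The trigger can also be read as a cycle running more than a week behind its planned date, which fits the stated purpose of the amendment. Either route holds drift to about 7 days. This stands. For the window, though, it requires counting from first dose: counted scan to scan, 3-day slips give 42 + 6 = 48 days, inside 49, and still accumulate.

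A site may sometimes satisfy both anchors. If ±1 week is applied to the scan days, two 7-day slips allow MIRV Cycle 4 Day 9 (78 + 8 = day 86, inside 77–91) and PLD Day 15 (99 + 14 = day 113, inside 105–119). With three slips this fails: 85 + 8 = day 93 and 106 + 14 = day 120.

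The 7-day case needs near-maximal slips at almost every cycle. Under Protocol 3.7 a missed SL-172154 dose is skipped without delaying the cycle, so only PLD or MIRV delays contribute.

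A reader might infer that the delays systematically lengthen PFS. The illustration does not support that. Nor is CBR bounded above: SAP 7.2 sets only a minimum (11 or 15 weeks), so SD on a late scan still counts. TTR is affected only for responses first seen after the first scan. Cycle-linked scans also have a practical use, since they coincide with dosing visits.

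**Conclusion.** The gap is real and modest. The protocol gives two scan anchors, and the rule between them does not address cumulative delay. On the literal reading, the second scan can be 2–3 weeks late and the third 4–5 weeks late if every cycle start slips 7 days, or 6–9 and 12–15 days late at 3 days per cycle. These figures rest on assumed delays and on the cycle anchor prevailing; on the other available readings drift stops at about 7 days.

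It would go too far to say that the protocol allows scans to run weeks late, or that PFS is inflated. What the documents support is that scan dates can depend on toxicity-related delay and on a site's reading, that some subjects can lose SD of 12 or 16 weeks for CBR, and that the PFS missed-scan rule lacks a single calendar. The primary safety and RP2D objectives do not turn on this, but the correction is cheap enough to be worth making.

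**What to change.** In Protocol 6.1 footnote m, 6.2 footnote o and 6.11, schedule all post-baseline scans by calendar weeks from C1D1, at the existing intervals and ±1 week, regardless of dose delay or hold. State that the window is counted from C1D1. Delete the cycle-day anchors and the condition on a delay of more than one week. The CBR tables in SAP 7.2 and the missed-scan rule in SAP 7.5 can then be programmed against one calendar.

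The cost is a wording change and a site memo. Scans will not always coincide with a dosing visit, and subjects with many delays may have slightly more scans per cycle.
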